7.6 Dose Modification

This clinical trial protocol includes a single infusion of GSK1070806 and therefore no patient dose modifications or dose reductions will be allowed during the trial.

7.7 Treatment Schedule

7.7.1 Treatment Visit 3 (Day 1 – Week 1)

- Clinical assessment
- Vital signs (heart rate, blood pressure, oral body temperature (°C), respiratory rate) taken pre-dose, and at 30 minutes interval during infusion period and repeated at 30 minute intervals for a period of 3 hours post infusion (removal of needle). Weight (kg) to be measured pre-infusion only
- Physical exam to be performed by clinician
- Influenza risk screening (prior to treatment)
- Pregnancy test (for female's patients of childbearing potential only)
- 12-lead ECG pre-infusion and 60 mins post infusion
- Biochemistry bloods (see Section 7.8.8)
- Haematology bloods (see Section 7.8.8)
- Blood serum for PK (pre-infusion sample to be taken within 1 hour of start of infusion, end of infusion sample to be taken within 15 minutes of end of infusion, and one sample taken between 4 hours and 8 hours post infusion start, see Figure 3 Pharmacokinetics sample time points)
- Blood serum for PD (pre-infusion only)
- Bloods for FBC, INR, UE, LFT 2hrs post end of infusion period. See Table 3
- CDAI assessment
- Blood serum for Immunogenicity (pre dose) analysis.
- Patient Daily Diary
- GSK1070806 / or Matched Placebo infusion
- Faecal calprotectin (patient stool sample) (if available post infusion or within 24 hours post infusion)
- Adverse Event/SAE reporting
- Record of patient concomitant medication
- Genetics/pharmacogenomics sample for optional genetic research
- Blood sample (serum) for additional research

For infusion reaction management/concomitant medication associated with GSK1070806 see Section 8.1.1.3 and Section 7.11.

7.7.2 Treatment Visit 3a (Day 2-Week 1)

Treatment visit 3a visit may either be an clinic visit or a telephone visit. The two alternative visit schedules are described below;

7.7.2.1 In person visit – patient attends clinic

- Clinical assessment
- Vital signs (heart rate, blood pressure, oral body temperature (°C), respiratory rate)
- Physical exam to be performed by clinician
- Biochemistry bloods (see Section 7.8.8)
- Haematology bloods (see Section 7.8.8)
- Blood serum for PK (some patients at the Birmingham site may have a 24 hr (post end of infusion) PK if they agree to this)
- Blood serum for PD (some patients at the Birmingham site may have a 24 hr (post end of infusion) PD if they agree to this)
- Patient Daily Diary
- Adverse Event/SAE reporting
- Record of patient concomitant medication

7.7.2.2 Telephone visit - virtual clinic

- Clinical assessment
- Adverse event/SAE reporting
- Record of patient concomitant medication

7.7.3 Treatment compliance

GSK1070806 or matched placebo will be prepared by site in accordance with the pharmacy manual. The allocated treatment will be prepared by suitably qualified pharmacy personnel (detailed one the site delegation log) and labelled with the trial specific label in order to maintain the trial blind. Only the site pharmacy personnel will be unblinded to the trial medication. All other trial personnel within the site will be blind to the allocated treatment for each individual patient. The allotted trial medication will subsequently be stored and be administered intravenously (within a given timeframe) to subject as an infusion at the trial site in accordance with the pharmacy manual and local procedures.

The full and accurate record of drug preparation (batch numbers, and time of preparation, dispensing and time of actual administration) will be maintained within the individual site pharmacy file and subsequent treatment compliance. This information will be provided to the Sponsor upon request and some information will be recorded within the case report form. Full drug accountability records and infusion start/stop times, flow rates, reasons for any interruptions in drug delivery will be maintained by the participating site and some of this information will also be recorded within the case report form.

Please refer to the current CDAID Pharmacy Manual for further information.

7.7.4 Treatment Discontinuation

This clinical trial protocol includes a single infusion of GSK1070806 and therefore the potential for treatment discontinuation only occurs within this single infusion. If an infusion is interrupted, suspended or stopped – a full record of the circumstances, outcomes will be maintained by the participating site within the patient medical records and recorded in the appropriate case report form.

7.7.5 Treatment of Trial Treatment Overdose

For this trial, any dose of GSK1070806 > 10 mg/kg will be considered an overdose.

There are no known antidotes and as such there are no recommend specific treatments for an overdose. In the event of an overdose the Investigator will use clinical judgement in treating the symptoms and should:

- 1. Contact the CDAID Trial Office and/or designated Clinical Coordinator/ medical advisor immediately
- 2. Closely monitor the subject for AEs /SAEs and laboratory abnormalities per the Investigator's discretion for at least 24 weeks or twice the length of the anticipated biologic effect of the dose received.
- 3. Obtain a plasma sample for pharmacokinetic (PK) analysis within 2 days from the date of the trial treatment overdose if requested by the Investigator (determined on a case-by-case basis).
- 4. Document the quantity of the excess dose in the CRF.

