7. TREATMENT DETAILS

7.1 Investigational Medicinal Product Preparation

7.1.1 Experimental group

Product name:	GSK1070806
Active Substance	GSK1070806 – Humanised IgG1 antibody
Dosage form:	100 mg/mL injectable solution
Unit dose strength(s)/Dosage level(s):	Single dose of 10 mg/kg
Route of Administration	IV infusion
Dosing instructions:	Dilute into 100 mL sterile IV infusion bag 0.9% Sodium Chloride (details see Pharmacy Manual)

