7.3 Instructions for handling and preparation of Investigational Medicinal Product

A description of the methods and materials required for preparation of GSK1070806 is detailed in the Pharmacy Manual. Trial treatment must be dispensed or administered according to procedures described herein and in the Pharmacy Manual.

Only subjects enrolled in the trial may receive trial treatment. Only authorised site staff may supply or administer trial treatment. All trial treatment must be stored in a secure area with access limited to the Investigator and authorised site staff.

The Investigator is responsible for trial treatment, accountability, reconciliation, and record maintenance. The Investigator or the head of the medical institution (where applicable), or designated site staff (e.g., storage manager, where applicable) must maintain trial treatment accountability records throughout the course of the trial. The responsible person(s) will document the amount of trial treatment received from GSK (complete all appropriate procedures relating to the condition of the IMP/trial documentation; temperature logs etc.) and the amount administered to subjects. In addition to any excess stock disposed of in accordance with the local standard operating procedure for IMP disposal. The required accountability unit for this trial will be the vial. Discrepancies are to be reconciled or resolved. Procedures for final disposal of unused trial treatment are listed in the Pharmacy Manual.

Investigational product is not expected to pose significant occupational safety risk to site staff under normal conditions of use and administration. However, precautions are to be taken to avoid direct skin contact, eye contact, and generating aerosols or mists. In the case of unintentional occupational exposure notify the monitor, medical monitor and/or trial manager. A Material Safety Data Sheet describing occupational hazards and recommended handling precautions either will be provided to the Investigator, where this is required by local laws, or is available upon request from GSK/ Sponsor.

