7.8.9 Pharmacokinetics and Pharmacodynamics Sampling

Samples for PK and PD analysis will be taken at the following visits and time points outlined in Table 4, Table 5 and Figure 3 below.

Visit Number	Taken	Time point (if applicable)
3	х	Pre-dose
		End of infusion
		4-8h post infusion start
За	Х	To be taken if patient attends
4	X	
5	X	
6	Х	
7	Х	
8	Х	
9		
10	Х	

Table 6 Pharmacodynamics sampling

Visit Number	Taken	Time point (if applicable)
3	Х	Pre-dose
За	X	To be taken if patient attends
4	Х	
5	Х	
6	Х	
7	Х	
8	Х	
9	х	
10	Х	

Figure 3 Pharmacokinetics sample time points

Concentrations of GSK1070806 will be determined in serum samples using the currently approved bioanalytical methodology at Covance Laboratories (Harrogate UK).

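### The overdose cut-off equals the planned dose, and the overdose steps can reveal the active arm to the blinded Investigator and ask for plasma where the assay uses serum

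*Protocol*

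**What the plan says.** **Dose and cut-off.** Section 7.1.1 gives the dosage level as "Single dose of 10 mg/kg", and Table 1 in 7.5 repeats 10 mg/kg. Section 7.7.5 then states that "any dose of GSK1070806 > 10 mg/kg will be considered an overdose". No tolerance is given.

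**Preparation and weight.** The product is a "100 mg/mL injectable solution". Section 7.3 defers the rest: "A description of the methods and materials required for preparation of GSK1070806 is detailed in the Pharmacy Manual". The protocol itself has no rounding rule and does not say which weight sets the dose. For the dosing visit, 7.7.1 says "Weight (kg) to be measured pre-infusion only". Footnote 2 of the Schedule of Events places weight at Screening Visit 1 and a Visit 12. It does not name Visit 3, and the schedule ends at Visit 10.

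**Blinding.** Placebo is 0.9% sodium chloride (7.1.2). Section 7.7.3 says "Only the site pharmacy personnel will be unblinded to the trial medication". Yet 7.7.5 tells the Investigator to contact the Trial Office or Clinical Coordinator at once, to monitor the patient closely, and to enter the size of the excess in the CRF.

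**Sample.** Item 3 of 7.7.5 reads "Obtain a plasma sample for pharmacokinetic (PK) analysis within 2 days", if the Investigator requests it. Section 7.8.9 says "Concentrations of GSK1070806 will be determined in serum samples using the currently approved bioanalytical methodology". Sections 7.7.1 and 7.9.3.1 also refer to serum.

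**The concern.** Three things in 7.7.5 do not fit the rest of the protocol.

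- **No headroom.** With the cut-off equal to the target, a deviation of any size above 10 mg/kg is formally an overdose, including one produced only by preparation arithmetic. The protocol does not let a reader tell whether that is intended or how often it would arise.
- **Blinding.** Only a patient on GSK1070806 can exceed a GSK1070806 dose. An Investigator who reports an overdose and writes down its size therefore knows the allocation. Under 7.8.1 the clinical assessments cover AEs, which belong to the primary outcome, and CDAI, which is the key secondary outcome.
- **Matrix.** If the optional overdose sample is taken as written, it is not in the matrix that the concentration assay is stated to measure.

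The blinding and matrix points apply to a single genuine overdose and need no estimate of frequency.

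**Working it through.** The protocol states no expected number of overdoses, so there is no figure to reproduce. The check has four parts.

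**1. Headroom.** Cut-off minus planned dose = 10 − 10 = 0 mg/kg.

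**2. Share of active patients above 10 mg/kg.**

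Inputs from the protocol: 10 mg/kg; 100 mg/mL, so 0.1 mL holds 10 mg; 21 patients randomised 2:1, so 21 × 2/3 = 14 active and 7 placebo.

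Assumptions, not in the protocol: weights Normal with mean 72 kg and SD 15 kg, limited to 40–130 kg and recorded to 0.1 kg; and a range of rounding rules and weight changes.

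The size for 10 mg steps can be seen by hand. With weight to 0.1 kg, the exact dose (10 × weight) is a whole number of mg, and its last digit decides the rounding:

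- digits 1–4 go down, 6–9 go up, 0 is unchanged and 5 is a tie;
- nearest, ties up: 5/10 = 50% above; ties split evenly: 4.5/10 = 45%;
- always up: 9/10 = 90%; always down: 0%.

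Simulation under the assumed weights (2,000,000 draws, ties up) gave:

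| Case | Share above 10 mg/kg |
|---|---|
| Exact on the dosing weight, or always rounded down | 0% |
| Nearest 10, 50 or 100 mg | 49% |
| Always up to 10, 50 or 100 mg | 89%, 96%, 97% |
| Unrounded, earlier weight, mean change 0 (SD 0.5–2 kg) | 46–49% |
| Same, mean loss of 1 kg | 68–97% |
| Same, mean gain of 1 kg | 2–30% |

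The 10 mg results lie just under the hand values because weights set to the 40 or 130 kg limit need no rounding.

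The range is therefore about 0% to 97%. At 45–50%, the expected number is 14 × 0.45 = 6.3 to 14 × 0.50 = 7.0, and the chance of at least one is 1 − 0.55^14 = 0.9998 or more. At 0% it is none. On placebo it is none of 7 in every case.

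Size of the excess with nearest-10 mg rounding: at most 5 mg, which is largest relative to weight near 40 kg. For 40.5 kg, the exact dose of 405 mg becomes 410 mg, and 410/40.5 = 10.12 mg/kg, an excess of about 0.12 mg/kg. Coarser rounding gives more: the simulated maximum was 10.59 mg/kg at 50 mg steps and 11.11 mg/kg at 100 mg steps.

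**3. Blinding.**

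- 7.1.2: placebo contains no GSK1070806, so a dose above 10 mg/kg implies the active arm.
- 7.7.5: the Investigator reports the overdose, and the excess goes in the CRF.
- 9.1: the Investigator or a delegated member of the research team completes the CRF, and a copy goes in the site file. Table 9 lists no separate unblinded form.
- 7.7.3: nobody at site outside pharmacy should know the allocation.
- 8.2.7: a code break is for cases where care depends on knowing the drug. Under 8.2.7.1 the treating physician is not told the result of a code break done to classify a SUSAR.

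The steps in 7.7.5 cannot be carried out as written without giving the Investigator the arm, and 7.7.5 does not refer to 8.2.7.

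**4. Matrix.** Plasma in 7.7.5 item 3; serum in 7.7.1, 7.8.9 and 7.9.3.1.

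**The case against.** - **A target of 10 and an overdose above 10 do not contradict each other.** That is right. The point is the absence of headroom and the missing link to preparation, not a logical conflict.
- **The frequency is unknown.** A reader might infer that nearly half of correctly dosed active patients would be overdoses. The documents do not support this. That figure is the symmetric case, and any zero-mean error around a cut-off puts about half above it. The Pharmacy Manual is not shown. If it rounds down, or doses exactly on the pre-infusion weight in 7.7.1, the share is 0%.
- **The infusion figures may put the delivered dose lower.** At 80 mL/h for one hour (7.5), 80 mL of a 100 mL bag (7.1.1) is given: 10 × 80/100 = 8.0 mg/kg, or about 7.3–7.6 mg/kg if the drug volume is added to the 100 mL (100 kg down to 50 kg). This weakens any frequency claim. It is also a further discrepancy to reconcile, since 7.7.5 does not say whether dose means prepared or delivered.
- **Extra monitoring in the active arm.** A reader might infer that overdose monitoring adds a long period of AE follow-up in one arm. Largely it does not. AE reporting already runs to Day 168 (24 × 7) for everyone, safety bloods are taken at each visit, and overdose monitoring is at the Investigator's discretion. The PK sample is optional too.
- **The blinded Investigator would not know unless told.** This is fair for small preparation differences, because nothing obliges pharmacy to disclose rounding. It is therefore not shown that every excess would unblind someone. But 7.7.5 gives its actions to the Investigator, who can act only once told. In a genuine overdose, care may justify knowing the arm, and 8.2.7 already provides for that.
- **Plasma against serum is one word in an optional sample.** That is true, and it limits the weight of this part.

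**Conclusion.** The concern holds in a limited form. Three statements rest on the text alone: the overdose cut-off equals the planned dose with 0 mg/kg of headroom; the overdose steps, carried out by the blinded Investigator, identify the active arm, contrary to 7.7.3; and the overdose PK sample is not in the stated assay matrix.

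The number of patients affected is not a finding. It runs from 0% to about 97% of active patients depending on a rounding rule and a dosing weight that the protocol does not give, and every figure between rests on assumed body weights. Nor do the documents show that the CDAI or AE comparison would be biased to any particular degree. What they show is an instruction that can break the blind whenever it is used, with no safeguard stated in 7.7.5.

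**What to change.** - **Reconcile the dosing passages.** The sponsor should bring 7.7.5 into line with 7.1.1, 7.5, the weight instructions (Schedule of Events footnote 2 and 7.7.1) and the Pharmacy Manual. The text should make clear which weight and which dose, prepared or delivered, the overdose definition refers to. The bag volume and the infusion rate and time need the same treatment. No threshold, margin or dose is proposed here; those are for the sponsor.
- **Protect the blind.** Have unblinded pharmacy or trial staff report the overdose and record the excess outside the blinded CRF. The Investigator should be told under the code-break rule in 8.2.7 when patient care needs it, and 7.7.5 should refer to that rule.
- **Align the sample.** Make the overdose PK sample in item 3 match the serum assay in 7.8.9.

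The cost is wording in 7.7.5 and the Pharmacy Manual, plus a small amount of extra work for unblinded staff.

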7.7.6 Treatment after the end of the Trial

Patients will not be able to receive any additional infusions of GSK1070806 outside the single infusion of GSK1070806 or matched placebo included in the clinical trial protocol and after completion of the trial. All enrolled patients will be receiving standard of care applicable at site. The individual local site Investigator is responsible for ensuring that considerations has been given to the post-trial care of the patients' medical condition being studied in this trial.

7.8 Assessments

7.8.1 Clinical Assessment

All clinical assessments will be performed by a suitability qualified medical practitioner. The Patient Daily Diary, CDAI score and adverse events will be assessed. When asking patients questions during the examination appropriate care will be taken not to induce bias into any potential response. This is very important when assessing potential adverse events or discussing the treatment. Open ended and non-leading verbal questions will be used where possible i.e.:

- "How are you feeling?"
- "Have you had any (other) medical problems since your last visit/contact?"
- "Have you taken any new medicines, other than those provided in this study, since your last visit/contact?"

7.8.2 Vital Signs

All vital signs will be performed by a suitability qualified medical practitioner/research nurse and shall include:

- Heart rate
- Blood Pressure
- Weight (kg)
- Body temperature
- Respiratory Rate

7.8.3 Physical Examination

The need for a physical examination will be determined by the local Investigator according to clinical need. The result of any additional examination will be recorded in the patients' medical notes and appropriate sections of the case report forms.

7.8.4 Serology Screening

The following blood test will be performed within 12 months of the Screening visits in local laboratories at investigative sites.

Table 2 Serology Blood Tests

	Blood test	Primary reason for assessment
Serology	Hepatitis B surface antigen (HBsAg), (confirmed within 12 months of randomisation) or, Core antigen (HBcAg) or, Surface antibody (HBsAb)	Eligibility assessment
	Hepatitis C (qualitative enzyme immunoassay) test result.	Eligibility assessment

7.8.5 Influenza Risk Screening

A review of patients recent medical history will be performed by a suitability qualified medical practitioner/research nurse – specifically related to any current evidence, or history within the last 14 days, of an influenza-like illness as defined by fever (>38°C) and two or more of the following symptoms; cough, sore throat, runny nose, sneezing, limb/joint pain, headache, vomiting/diarrhoea. The Investigator will confirm if the symptoms are related to CD.

7.8.6 Clostridium Difficile Testing

Clostridium Difficile testing will be carried out as per local practice to confirm eligibility.

7.8.7 Pregnancy Test

A pregnancy test should be performed for all women of child bearing potential within 14 days of expected day 1 of treatment (both urine or serum pregnancy tests are acceptable).

7.8.8 Biochemistry and Haematology

The following blood tests will be performed at each visit. Tests used for safety laboratory assessments will be done in local laboratories at investigative sites.

Table 3: Blood Tests

	Blood test	Primary reason for assessment
Biochemistry	Alkaline Phosphatase (ALP)	Safety
	Alanine Transaminase (ALT)	
	Aspartate Transaminase (AST)	
	Albumin	
	Bilirubin	
	Sodium	
	Potassium	
	Urea	
	Creatinine	

	Calcium	
	Total Protein	
	*Estimated Glomerular Filtration Rate (eGFR)	
	C-Reactive Protein	
Haematology	Haemoglobin	Safety
	Platelets	
	Red Blood Cells	
	White Blood Cells	
	Haematocrit	
	Mean Cell Volume	
	Mean Cell Haemoglobin	
	Neutrophils	
	Lymphocytes	
	Monocytes	
	Eosinophils	
	Basophils	
	INR	
	APTT Ratio	

*- calculated by Cockcroft-Gault equation or alternative as per institutional practice – Appendix 7

Only in the event of suspected Cytokine release syndrome adverse event: the following blood tests will need to be performed to confirm adverse event. These tests are considered as part of standard care when investigating this specific syndrome. Please see the Laboratory Manual for further details.

Table 4 Immunology blood tests

Immunology	TNF- α	Safety
	IFN-Y	
	IL-6	

7.8.9 Pharmacokinetics and Pharmacodynamics Sampling

Samples for PK and PD analysis will be taken at the following visits and time points outlined in Table 4, Table 5 and Figure 3 below.

Visit Number	Taken	Time point (if applicable)
3	х	Pre-dose
		End of infusion
		4-8h post infusion start
За	Х	To be taken if patient attends
4	X	
5	X	
6	Х	
7	Х	
8	Х	
9		
10	Х	

Table 6 Pharmacodynamics sampling

Visit Number	Taken	Time point (if applicable)
3	Х	Pre-dose
За	X	To be taken if patient attends
4	Х	
5	Х	
6	Х	
7	Х	
8	Х	
9	х	
10	Х	

Figure 3 Pharmacokinetics sample time points

Concentrations of GSK1070806 will be determined in serum samples using the currently approved bioanalytical methodology at Covance Laboratories (Harrogate UK).

7.8.10 Endoscopy with Biopsy

Endoscopies will be performed during screening and at week 12 after dosing. This is standard of care procedure in CD. Colonoscopic assessment after drug administration to check endoscopic response is also often part of standard clinical practice. Up to 12 biopsies will be taken from the lesioned and non-lesioned region of the tissue at the pre-dose visit and at week 12 post treatment with GSK1070806. Endoscopies will include the capture of photographic images and/or video recordings. All endoscopies will be reviewed by a central reviewer who is blinded.

7.8.11 Crohn's Disease Activity Index

The following address was correct when the version of the protocol was approved: http://www.igibdscores.it/en/score-cdai.html

7.8.12 Immunogenicity Blood Sample

For all patients, blood samples for the determination of Anti-drug Antibodies (ADA) will be collected as is scheduled in the Schedule of Events table. Please see the Laboratory Manual for further information.

7.8.13 Patient Daily Diary

The Patient Daily Diary will be given to the patient at every visit and reviewed by the Investigator.

